6.1. Study Endpoints

Safety Endpoints:

- Frequency and severity of treatment-emergent AEs, AEs of special interest, and SAEs
- Frequency of laboratory abnormalities
- Change from baseline vital signs
- Frequency of cardiac rhythm abnormalities

6.2. Analysis Populations

Four analysis populations are defined in this study:

- Intention-to-treat (ITT) Population: all randomized subjects regardless of whether they receive study drug, with analyses conducted according to the randomized treatment assignment
- Safety Analysis Population: all randomized subjects who receive at least 1 dose of study drug, with analyses conducted by actual treatment received
- PK Analysis Population: all randomized subjects who receive at least 1 dose of study

6.3. Covariates and Subgroups

The study is not adequately powered to detect treatment differences in any subgroup analysis. Any subgroup analyses performed will be considered exploratory.

6.4. Missing Data

In general, no imputation of missing data will be done in the study unless specifically stated in this SAP. For mixed model repeated measure analyses, missing data are handled by the model implicitly. For responder analyses, if the patient's responder status cannot be determined due to missing data, the patient will be treated as non-responder. For other analyses, missing data will not be included in the analyses.

Handling of Missing Data:

- In general, missing result values will not be imputed unless otherwise specified.
- For values below the lower limit of quantitation (LLOQ), 1/2 of LLOQ will be imputed unless otherwise specified.
- In general, for missing or partial dates the following noted:
 - Start Dates:
 - If day is missing, then impute it to be the start of the month (e.g., 01MMMYYYY), except if the month and year is equal to the first dose date month and year then impute the day to be the same day as the first dose date.
 - If month is missing, then impute it to be the start of the year (e.g., 01JANYYYY), except if the year is equal to the first dose date year then impute the day and month to be the same as the first dose date.
 - If year is missing, then do not impute.
 - End Dates:
 - If day is missing, then impute it to be the end of the month (e.g., 31MMMYYYY), except if the month and year is equal to the last assessment date month and year then the day should be imputed to the last assessment date day.
 - If month is missing, then impute it to be the end of the year (e.g., 31DECYYYY), except if the year is equal to the last assessment date year then the day and month should be imputed to the last assessment date day and month.
 - If year is missing, then do not impute.

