## **11.2 Adverse Event Reporting and Descriptions**

### ***11.2.1 Reporting Period and Follow-up***

#### **11.2.1.1 Adverse Events**

AEs will be assessed from the time the participant provides informed consent through the duration of the study. Preexisting medical conditions that increase in severity from the first dose of study medication will be reported as AEs. Preexisting medical conditions that increase in severity after providing informed consent but before the first dose of study medication will be reported as medical history.

Any AEs that are unresolved at the participant's last visit in the study will be followed by the investigator until resolved or stabilized and are considered irreversible, or the participant has died.

MyoKardia retains the right to request additional information for any participant with ongoing AE(s)/SAE(s) at the end of the study, if judged necessary.

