13.1. Adverse Events

AEs will be mapped to system organ classes and preferred terms using the Medical Dictionary for Regulatory Activities (MedDRA v21.0). AEs will be monitored during the study and the data analyzed with respect to overall incidence as well as severity and potential relationship of AEs to study medication. AEs with onset during the treatment-emergent period or with an onset before the first dose of study medication that increases in severity or becomes serious during the treatment-emergent period, will be considered treatment-emergent.

Adverse event incidence tables will present the number (n) and percentage (%) of subjects experiencing at least one treatment-emergent AE (TEAE) by system organ class (SOC) and preferred term (PT). Multiple occurrences of the same event in the same patient will be counted only once in the tables. The denominator for computation of percentages is the safety population within each treatment group. In addition, the adverse event incident table will also be presented by SOC, PT, and severity grade. When there are multiple occurrences of the same event in the same patient, only the most severe one will be included in the tables.

Adverse event incidence tables will be provided by treatment group for all types of TEAEs: all TEAEs, all treatment-emergent serious AEs, drug related AEs, AEs of Special Interest (AESI; per protocol), all TEAEs leading to permanent treatment discontinuation, and all TEAEs leading to death.

AE may also be summarized by Standardised MedDRA Queries (SMQs) deemed relevant based on AESIs and SAEs observed in the study.

A by-subject listing of all AEs, SAEs, and TEAEs leading to treatment discontinuation will also be provided.

Deaths

The following deaths summaries will be generated in a summary table and listed in a by-subject data listing:

- Number and percent of subjects who died by study period (TEAE, on-study) summarized on the safety population by treatment received
- Death in non-randomized subjects or randomized and not treated subjects
- TEAE leading to death (death as an outcome on the AE eCRF page as reported by the investigator) by primary SOC and PT showing number and percent of subjects

Pregnancy

The following pregnancy information will be provided in a by-subject data listing:

- Number of subjects or partners of subjects who became pregnant summarized by treatment received
- Outcomes of the pregnancies and analysis of the outcomes

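### The partial-date rule in SAP 6.4 ignores the end date, so an adverse event recorded as over before first dose can be counted as treatment-emergent

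*SAP*

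**What the plan says.** SAP 6.4 introduces its date rules as general ones: "In general, for missing or partial dates the following noted". For start dates:

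- **Day missing.** The default is the first of the month. In the month and year of first dose the exception applies: "then impute the day to be the same day as the first dose date".
- **Month missing.** The default is 1 January. The exception is worded in parallel and again points to the day of first dose: "except if the year is equal to the first dose date year then impute the day and month to be the same as the first".
- **Year missing.** "If year is missing, then do not impute".

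None of these clauses mentions the end date of the record.

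SAP 13.1 counts as treatment-emergent "AEs with onset during the treatment-emergent period or with an onset before the first dose of study medication that increases in severity"; a pre-dose event that turns serious within the period also qualifies. SAP 13 defines the period as first dose to last dose plus 56 days. The end date plays no part in the definition, and the visible text of 13.1 has no date rule of its own for AEs.

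AEs can be on file before dosing. Protocol 11.2.1.1 states: "AEs will be assessed from the time the participant provides informed consent through the duration of the study". Screening runs from Day -28 to Day -1 (Protocol Table 1).

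**The concern.** The two first-dose exceptions resolve an unknown onset in favour of treatment-emergent status. That is reasonable when the record leaves the question open. When the recorded end date is before first dose, it is not open: the event was over before any drug was given. The rule still moves the onset to the day of first dose. This creates a record that starts after it ends, and it puts an event that cannot be treatment-emergent into the treatment-emergent tables.

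The tables affected report the frequency of treatment-emergent AEs. SAP 6.1 lists this as a safety endpoint, and it serves the study's objective of safety and tolerability (SAP 2.1). With about 20 subjects per group, one misplaced subject is visible in a table cell.

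**Working it through.** The plan gives no figure on this point, so there is none to reproduce. The check applies the rule as written to test dates, then asks in which direction it can err, how many records are exposed, and what one error is worth.

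**1. Test dates.** Illustrative first dose 20 June 2018; last dose 111 days later (Day 112).

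| Case | Recorded start | Recorded end | Start under SAP 6.4 | Treatment-emergent under SAP 13.1? |
|---|---|---|---|---|
| a | ?? June 2018 | 10 June 2018 | 20 June 2018 | Yes: wrong, start is 10 days after end |
| b | ?? May 2018 | 28 May 2018 | 1 May 2018 | No: right |
| c | ?? ??? 2018 | 28 May 2018 | 20 June 2018 | Yes: wrong, start is after end |
| d | ?? July 2018 | not given | 1 July 2018 | Yes: right |
| e | year missing | not given | none | Not defined |

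**2. Direction.** Take an event that truly began in the treatment-emergent period and whose start year is known.

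- If the partial date matches the first-dose month or year, the start becomes the first dose date, which is inside the period.
- If it lies in a later month or year, the start becomes the first day of that month or year. That day is after first dose and no later than the true onset.

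Either way the event stays treatment-emergent. In 400,000 simulated dates, 0% of such events were lost. The imputation can over-count but cannot under-count.

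**3. Exposure.** Assume pre-dose onset uniform over the 28 screening days and first dose uniform over the calendar.

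- *Day missing, 30-day month.* With first dose on day *d*, the share of the 28 days that falls in the same month is min(*d* − 1, 28)/28. Averaged over *d* = 1 to 30: (0 + 1 + … + 28 + 28)/(30 × 28) = 434/840 = 0.517. The simulation with true month lengths gave 0.523.
- *Day and month missing.* The same average over 365 days is (406 + 336 × 28)/(365 × 28) = 9,814/10,220 = 0.960. The simulation also gave 0.960.

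So about 52% of pre-dose AEs with only the day missing, and about 96% with day and month missing, are moved to the first dose date.

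**4. Size of one error.** SAP 13.1 counts subjects. One subject is 1/20 = 5 percentage points in a group of about 20 (SAP 5), or 1/40 = 2.5 points in the pooled active group.

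**The case against.** The strongest case for leaving the rule alone is that it will hardly ever matter.

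- A pre-dose change in a baseline condition goes to medical history unless a study procedure caused it (Protocol Table 1, footnote d; also Protocol 11.2.1.1), so few pre-dose AEs will be on file.
- Incomplete or inconsistent entries are queried (Protocol 14.2.3). AEs are asked about at every contact, with a question that refers back to the last one (Protocol 11.2.2.1), which helps to bound onset.
- The error needs a combination: a pre-dose AE, a partial start date, and an end date known well enough to be placed before first dose.
- These events precede treatment, so randomisation should spread them evenly on average. SAP 13 plans no hypothesis tests on safety.
- When the end date is missing or falls on or after first dose, moving the onset to first dose is a defensible cautious choice.

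All of this stands, and it limits the size of the point. It does not justify the result in cases a and c, where data already recorded show the classification to be wrong.

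Three stronger readings are tempting, and the documents do not support them.

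- *Errors in both directions.* A reader might infer that AEs with a missing start year drop out, because SAP 6.4 also says "For other analyses, missing data will not be included in the analyses". SAP 13.1 does not apply that default to undated AEs, and such events would still appear in the by-subject listing of all AEs. They are unclassified, which is a gap, but no under-count is shown.
- *Damage to a primary endpoint.* Only the objective is called primary. Treatment-emergent AE frequency is listed as a safety endpoint.
- *An error rate of 52%.* That figure is the share of day-missing pre-dose AEs exposed to the rule. An exposed event is provably misclassified only if its known end date is before first dose, and the documents give no basis for estimating how often that occurs.

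**Conclusion.** The point holds as a minor error in a stated rule. An AE with a partial start in the first-dose month (day missing) or first-dose year (month missing), and a recorded end before first dose, is given a start after its end and counted as treatment-emergent.

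The effect is over-counting only. Each affected subject adds at most 5 percentage points to a cell in a group of 20, or 2.5 in the pooled active group of 40, and nothing if that subject is already counted in the cell. Few events are expected, and no systematic difference between arms.

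The misclassification follows from the text alone. The exposure shares rest on the uniform-date assumptions. The expectation of few events rests on the medical-history routing and data queries, not on a count. The conclusion also assumes that no redacted part of the SAP overrides the rule for AEs.

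**What to change.** In SAP 6.4, add one condition to both start-date exceptions: apply them only when the end date is missing or could fall on or after first dose. Judge a partial end date by its recorded month and year, before any end-date imputation. When the end date is known to precede first dose, use the default start of month or start of year.

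Case a then starts on 1 June and case c on 1 January, and neither is treatment-emergent. This works in general: if the event ended before first dose, the first day of its start month or year is no later than its end, so the imputed start precedes first dose and cannot follow the end. Records with a missing or later end date are handled as now.

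As a secondary clarification, state that an AE with an unknown start year counts as treatment-emergent unless its end date precedes first dose.

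The cost is two sentences in the SAP and a small change to the date-derivation program. No new data and no protocol change are needed.

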6.5. Multiplicity Control

Due to the exploratory nature of the study, multiplicity adjustment is not planned.

7. SUBJECT DISPOSITION

The number and percentage of subjects who complete and discontinue the treatment and study as well as reasons for early discontinuation will be summarized by randomized treatment assignment using the ITT population.

7.1. Demographics and Baseline Characteristics

Demographic and baseline characteristics will be summarized descriptively by randomized treatment assignment using the ITT population.

Body surface area (BSA) will be derived using the Du Bois method.

CYP2C19 genotypes and phenotypes will be summarized as part of the baseline characteristics summary table and listing.

7.2. Extent of Study Treatment Exposure and Compliance

The extent of study treatment exposure and compliance will be assessed and summarized by actual treatment received within the safety population.

The duration of study drug exposure is defined as last dose date – first dose date + 1 day, regardless of intermittent discontinuations.

Compliance will be calculated based on the total cumulative dose received divided by the total planned cumulative dose. Imputation will be performed for subjects with missing or incomplete data.

Treatment compliance and above-planned and under-planned dosing percentages will be summarized descriptively (number [n], mean, SD, median, minimum, and maximum). The subjects with compliance < 80% will be fully described and summarized. In addition, number and percentage of subjects with at least 1 dosing administration will be given, as well as the number and percentage of subjects with 0, 0 to 20%, and greater than 20% under-planned dosing administrations.

Actual dose adjustments that occurred in the study and expected dose adjustments based on the criteria per protocol will be listed by subject and timepoint. Any inconsistencies will be flagged.

7.3. Protocol Deviations

Prior to database lock, all protocol deviations will be reviewed and confirmed by the Sponsor. All protocol deviations will be presented in a by-subject data listing. Important Protocol Deviations (IPD) (ie. CSR Reportable PDs) will be identified by the Sponsor and summarized in table. ICH E3 defines important protocol deviations as a subset of protocol deviations that may significantly impact the completeness, accuracy, and/or reliability of the study data or that may significantly affect a subject's rights, safety, or well-being.

For more information, contact the Office of the Vice President for Research and Economic Development at [contact] or [contact].

11. **What is the primary purpose of the *Journal of Clinical Endocrinology and Metabolism*?**

© 2013 Pearson Education, Inc. All Rights Reserved. May not be copied, scanned, or duplicated, in whole or in part. Due to electronic rights, some third party content may be suppressed from the eBook and/or eChapter(s). Editorial review has determined that any suppressed content does not materially affect the overall learning experience. Pearson Education, Inc. reserves the right to remove additional content at any time if subsequent rights restrictions require it.

the first time in the history of the world, the *whole* of the human race, in all its parts, has been gathered together, and is now to be seen in one place. The *whole* of the human race, in all its parts, is now to be seen in one place.

1. **What is the primary purpose of the proposed legislation?**

A large black rectangular box used to redact sensitive information from the document.

113. *Leptodora* (Leptodora) *hirsutissima* (L.) Schlecht. (1854) 113. *Leptodora* (Leptodora) *hirsutissima* (L.) Schlecht. (1854)

11. **What is the primary purpose of the *Journal of Clinical Endocrinology and Metabolism*?**

11. **What is the primary purpose of the *Journal of Clinical Endocrinology and Metabolism*?**

1

A series of 12 horizontal bar charts showing the percentage of the population aged 65 and over in each state and the District of Columbia. The bars are black with white outlines. The y-axis is labeled 'State' and the x-axis is labeled 'Percentage' with a scale from 0 to 20. The bars are ordered from highest percentage (top) to lowest (bottom).

State	Percentage
Florida	19.4
Massachusetts	18.9
Alabama	18.5
Mississippi	18.3
South Dakota	18.2
North Dakota	18.1
Arkansas	17.9
Illinois	17.8
Michigan	17.7
Washington	17.6
Wyoming	17.5
Missouri	17.4
Virginia	17.3
West Virginia	17.2
Utah	17.1
Arizona	17.0
Colorado	16.9
Montana	16.8
North Carolina	16.7
Nebraska	16.6
South Carolina	16.5
Alaska	16.4
Tennessee	16.3
Louisiana	16.2
Georgia	16.1
Connecticut	16.0
Indiana	15.9
Pennsylvania	15.8
Michigan	15.7
Ohio	15.6
Virginia	15.5
Mississippi	15.4
Alabama	15.3
North Carolina	15.2
South Carolina	15.1
Arkansas	15.0
Missouri	14.9
Illinois	14.8
Michigan	14.7
West Virginia	14.6
Wyoming	14.5
Utah	14.4
Arizona	14.3
Colorado	14.2
Montana	14.1
North Dakota	14.0
South Dakota	13.9
Arkansas	13.8
Mississippi	13.7
Alabama	13.6
Missouri	13.5
Illinois	13.4
Michigan	13.3
West Virginia	13.2
Wyoming	13.1
Utah	13.0
Arizona	12.9
Colorado	12.8
Montana	12.7
North Dakota	12.6
South Dakota	12.5
Arkansas	12.4
Mississippi	12.3
Alabama	12.2
Missouri	12.1
Illinois	12.0
Michigan	11.9
West Virginia	11.8
Wyoming	11.7
Utah	11.6
Arizona	11.5
Colorado	11.4
Montana	11.3
North Dakota	11.2
South Dakota	11.1
Arkansas	11.0
Mississippi	10.9
Alabama	10.8
Missouri	10.7
Illinois	10.6
Michigan	10.5
West Virginia	10.4
Wyoming	10.3
Utah	10.2
Arizona	10.1
Colorado	10.0
Montana	9.9
North Dakota	9.8
South Dakota	9.7
Arkansas	9.6
Mississippi	9.5
Alabama	9.4
Missouri	9.3
Illinois	9.2
Michigan	9.1
West Virginia	9.0
Wyoming	8.9
Utah	8.8
Arizona	8.7
Colorado	8.6
Montana	8.5
North Dakota	8.4
South Dakota	8.3
Arkansas	8.2
Mississippi	8.1
Alabama	8.0
Missouri	7.9
Illinois	7.8
Michigan	7.7
West Virginia	7.6
Wyoming	7.5
Utah	7.4
Arizona	7.3
Colorado	7.2
Montana	7.1
North Dakota	7.0
South Dakota	6.9
Arkansas	6.8
Mississippi	6.7
Alabama	6.6
Missouri	6.5
Illinois	6.4
Michigan	6.3
West Virginia	6.2
Wyoming	6.1
Utah	6.0
Arizona	5.9
Colorado	5.8
Montana	5.7
North Dakota	5.6
South Dakota	5.5
Arkansas	5.4
Mississippi	5.3
Alabama	5.2
Missouri	5.1
Illinois	5.0
Michigan	4.9
West Virginia	4.8
Wyoming	4.7
Utah	4.6
Arizona	4.5
Colorado	4.4
Montana	4.3
North Dakota	4.2
South Dakota	4.1
Arkansas	4.0
Mississippi	3.9
Alabama	3.8
Missouri	3.7
Illinois	3.6
Michigan	3.5
West Virginia	3.4
Wyoming	3.3
Utah	3.2
Arizona	3.1
Colorado	3.0
Montana	2.9
North Dakota	2.8
South Dakota	2.7
Arkansas	2.6
Mississippi	2.5
Alabama	2.4
Missouri	2.3
Illinois	2.2
Michigan	2.1
West Virginia	2.0
Wyoming	1.9
Utah	1.8
Arizona	1.7
Colorado	1.6
Montana	1.5
North Dakota	1.4
South Dakota	1.3
Arkansas	1.2
Mississippi	1.1
Alabama	1.0
Missouri	0.9
Illinois	0.8
Michigan	0.7
West Virginia	0.6
Wyoming	0.5
Utah	0.4
Arizona	0.3
Colorado	0.2
Montana	0.1
North Dakota	0.0
South Dakota	0.0
Arkansas	0.0
Mississippi	0.0
Alabama	0.0
Missouri	0.0
Illinois	0.0
Michigan	0.0
West Virginia	0.0
Wyoming	0.0
Utah	0.0
Arizona	0.0
Colorado	0.0
Montana	0.0
North Dakota	0.0
South Dakota	0.0
Arkansas	0.0
Mississippi	0.0
Alabama	0.0
Missouri	0.0
Illinois	0.0
Michigan	0.0
West Virginia	0.0
Wyoming	0.0
Utah	0.0
Arizona	0.0
Colorado	0.0
Montana	0.0
North Dakota	0.0
South Dakota	0.0
Arkansas	0.0
Mississippi	0.0
Alabama	0.0
Missouri	0.0
Illinois	0.0
Michigan	0.0
West Virginia	0.0
Wyoming	0.0
Utah	0.0
Arizona	0.0
Colorado	0.0
Montana	0.0
North Dakota	0.0
South Dakota	0.0
Arkansas	0.0
Mississippi	0.0
Alabama	0.0
Missouri	0.0
Illinois	0.0
Michigan	0.0
West Virginia	0.0
Wyoming	0.0
Utah	0.0
Arizona	0.0
Colorado	0.0
Montana	0.0
North Dakota	0.0
South Dakota	0.0
Arkansas	0.0
Mississippi	0.0
Alabama	0.0
Missouri	0.0
Illinois	0.0
Michigan	0.0
West Virginia	0.0
Wyoming	0.0
Utah	0.0
Arizona	0.0
Colorado	0.0
Montana	0.0
North Dakota	0.0
South Dakota	0.0
Arkansas	0.0
Mississippi	0.0
Alabama	0.0
Missouri	0.0
Illinois	0.0
Michigan	0.0
West Virginia	0.0
Wyoming	0.0
Utah	0.0
Arizona	0.0
Colorado	0.0
Montana	0.0
North Dakota	0.0
South Dakota	0.0
Arkansas	0.0
Mississippi	0.0
Alabama	0.0
Missouri	0.0
Illinois	0.0
Michigan	0.0
West Virginia	0.0
Wyoming	0.0
Utah	0.0
Arizona	0.0
Colorado	0.0
Montana	0.0
North Dakota	0.0
South Dakota	0.0
Arkansas	0.0
Mississippi	0.0
Alabama	0.0
Missouri	0.0
Illinois	0.0
Michigan	0.0
West Virginia	0.0
Wyoming	0.0
Utah	0.0
Arizona	0.0
Colorado	0.0
Montana	0.0
North Dakota	0.0
South Dakota	0.0
Arkansas	0.0
Mississippi	0.0
Alabama	0.0
Missouri	0.0
Illinois	0.0
Michigan	0.0
West Virginia	0.0
Wyoming	0.0
Utah	0.0
Arizona	0.0
Colorado	0.0
Montana	0.0
North Dakota	0.0
South Dakota	0.0
Arkansas	0.0
Mississippi	0.0
Alabama	0.0
Missouri	0.0
Illinois	0.0
Michigan	0.0
West Virginia	0.0
Wyoming	0.0
Utah	0.0
Arizona	0.0
Colorado	0.0
Montana	0.0
North Dakota	0.0
South Dakota	0.0
Arkansas	0.0
Mississippi	0.0
Alabama	0.0
Missouri	0.0
Illinois	0.0
Michigan	0.0
West Virginia	0.0
Wyoming	0.0
Utah	0.0
Arizona	0.0
Colorado	0.0
Montana	0.0
North Dakota	0.0
South Dakota	0.0
Arkansas	0.0
Mississippi	0.0
Alabama	0.0
Missouri	0.0
Illinois	0.0
Michigan	0.0
West Virginia	0.0
Wyoming	0.0
Utah	0.0
Arizona	0.0
Colorado	0.0
Montana	0.0
North Dakota	0.0
South Dakota	0.0
Arkansas	0.0
Mississippi	0.0
Alabama	0.0
Missouri	0.0
Illinois	0.0
Michigan	0.0
West Virginia	0.0
Wyoming	0.0
Utah	0.0
Arizona	0.0
Colorado	0.0
Montana	0.0
North Dakota	0.0
South Dakota	0.0
Arkansas	0.0
Mississippi	0.0
Alabama	0.0
Missouri	0.0
Illinois	0.0
Michigan	0.0
West Virginia	0.0
Wyoming	0.0
Utah	0.0
Arizona	0.0
Colorado	0.0
Montana	0.0
North Dakota	0.0
South Dakota	0.0
Arkansas	0.0
Mississippi	0.0
Alabama	0.0
Missouri	0.0
Illinois	0.0
Michigan	0.0
West Virginia	0.0
Wyoming	0.0
Utah	0.0
Arizona	0.0
Colorado	0.0
Montana	0.0
North Dakota	0.0
South Dakota	0.0
Arkansas	0.0
Mississippi	0.0
Alabama	0.0
Missouri	0.0
Illinois	0.0
Michigan	0.0
West Virginia	0.0
Wyoming	0.0
Utah	0.0
Arizona	0.0
Colorado	0.0
Montana	0.0
North Dakota	0.0
South Dakota	0.0
Arkansas	0.0
Mississippi	0.0
Alabama	0.0
Missouri	0.0
Illinois	0.0
Michigan	0.0
West Virginia	0.0
Wyoming	0.0
Utah	0.0
Arizona	0.0
Colorado	0.0
Montana	0.0
North Dakota	0.0
South Dakota	0.0
Arkansas	0.0
Mississippi	0.0
Alabama	0.0
Missouri	0.0
Illinois	0.0
Michigan	0.0
West Virginia	0.0
Wyoming	0.0
Utah	0.0
Arizona	0.0
Colorado	0.0
Montana	0.0
North Dakota	0.0
South Dakota	0.0
Arkansas	0.0
Mississippi	0.0
Alabama	0.0
Missouri	0.0
Illinois	0.0
Michigan	0.0
West Virginia	0.0
Wyoming	0.0
Utah	0.0
Arizona	0.0
Colorado	0.0
Montana	0.0
North Dakota	0.0
South Dakota	0.0
Arkansas	0.0
Mississippi	0.0
Alabama	0.0
Missouri	0.0
Illinois	0.0
Michigan	0.0
West Virginia	0.0
Wyoming	0.0
Utah	0.0
Arizona	0.0
Colorado	0.0
Montana	0.0
North Dakota	0.0
South Dakota	0.0
Arkansas	0.0
Mississippi	0.0
Alabama	0.0
Missouri	0.0
Illinois	0.0
Michigan	0.0
West Virginia	0.0
Wyoming	0.0
Utah	0.0
Arizona	0.0
Colorado	0.0
Montana	0.0
North Dakota	0.0
South Dakota	0.0
Arkansas	0.0
Mississippi	0.0
Alabama	0.0
Missouri	0.0
Illinois	0.0
Michigan	0.0
West Virginia	0.0
Wyoming	0.0
Utah	0.0
Arizona	0.0
Colorado	0.0
Montana	0.0
North Dakota	0.0
South Dakota	0.0
Arkansas	0.0
Mississippi	0.0
Alabama	0.0
Missouri	0.0
Illinois	0.0
Michigan	0.0
West Virginia	0.0
Wyoming	0.0
Utah	0.0
Arizona	0.0
Colorado	0.0
Montana	0.0
North Dakota	0.0
South Dakota	0.0
Arkansas	0.0
Mississippi	0.0
Alabama	0.0
Missouri	0.0
Illinois	0.0
Michigan	0.0
West Virginia	0.0
Wyoming	0.0
Utah	0.0
Arizona	0.0
Colorado	0.0
Montana	0.0
North Dakota	0.0
South Dakota	0.0
Arkansas	0.0
Mississippi	0.0
Alabama	0.0
Missouri	0.0
Illinois	0.0
Michigan	0.0
West Virginia	0.0
Wyoming	0.0
Utah	0.0
Arizona	0.0
Colorado	0.0
Montana	0.0
North Dakota	0.0
South Dakota	0.0
Arkansas	0.0
Mississippi	0.0
Alabama	0.0
Missouri	0.0
Illinois	0.0
Michigan	0.0
West Virginia	0.0
Wyoming	0.0
Utah	0.0
Arizona	0.0
Colorado	0.0
Montana	0.0
North Dakota	0.0
South Dakota	0.0
Arkansas	0.0
Mississippi	0.0
Alabama	0.0
Missouri	0.0
Illinois	0.0
Michigan	0.0
West Virginia	0.0
Wyoming	0.0
Utah	0.0
Arizona	0.0
Colorado	0.0
Montana	0.0
North Dakota	0.0
South Dakota	0.0
Arkansas	0.0
Mississippi	0.0
Alabama	0.0
Missouri	0.0
Illinois	0.0
Michigan	0.0
West Virginia	0.0
Wyoming	0.0
Utah	0.0
Arizona	0.0
Colorado	0.0
Montana	0.0
North Dakota	0.0
South Dakota	0.0
Arkansas	0.0
Mississippi	0.0
Alabama	0.0
Missouri	0.0
Illinois	0.0
Michigan	0.0
West Virginia	0.0
Wyoming	0.0
Utah	0.0
Arizona	0.0
Colorado	0.0
Montana	0.0
North Dakota	0.0
South Dakota	0.0
Arkansas	0.0
Mississippi	0.0
Alabama	0.0
Missouri	0.0
Illinois	0.0
Michigan	0.0
West Virginia	0.0
Wyoming	0.0
Utah	0.0
Arizona	0.0
Colorado	0.0
Montana	0.0
North Dakota	0.0
South Dakota	0.0
Arkansas	0.0
Mississippi	0.0
Alabama	0.0
Missouri	0.0
Illinois	0.0
Michigan	0.0
West Virginia	0.0
Wyoming	0.0
Utah	0.0
Arizona	0.0
Colorado	0.0
Montana	0.0
North Dakota	0.0
South Dakota	0.0
Arkansas	0.0
Mississippi	0.0
Alabama	0.0
Missouri	0.0
Illinois	0.0
Michigan	0.0
West Virginia	0.0
Wyoming	0.0
Utah	0.0
Arizona	0.0
Colorado	0.0
Montana	0.0
North Dakota	0.0
South Dakota	0.0
Arkansas	0.0
Mississippi	0.0
Alabama	0.0
Missouri	0.0
Illinois	0.0
Michigan	0.0
West Virginia	0.0
Wyoming	0.0
Utah	0.0
Arizona	0.0
Colorado	

A large black rectangular redaction box covers the majority of the page content, starting below the header and ending above the footer. The redaction is not perfectly uniform, showing some internal white space and slight irregularities at the edges, particularly on the right side where it appears to be cut off by the page's edge.

This figure is a complex, abstract black and white diagram. It features numerous horizontal bars of varying lengths and vertical lines. The bars are primarily black on a white background, with some white bars interspersed. The diagram is highly abstract and lacks a clear title or descriptive text.

